9.7.1.1 Study Endpoints

PRIMARY ENDPOINT(S)

Cohort 1 (Single-Agent Dose-Finding)

- RD based on the TiTE-CRM design.

Cohort 2 (Single-Agent Expansion)

- Cohort 2A: DTC Group: ORR (CR + PR) for subjects with measurable disease and BOR for all subjects based on RECIST 1.1
- Cohort 2B: Osteosarcoma Group: PFS-4, ie, the percentage of subjects who are alive and free of disease progression 4 months after the first dose based on RECIST 1.1

Cohort 3A (Combination Dose-Finding)

- RD of the combination treatment (lenvatinib + ifosfamide + etoposide)

Cohort 3B (Combination Expansion)

- PFS-4, ie, the percentage of subjects who are alive and free of disease progression 4 months after the first dose based on RECIST 1.1

SECONDARY ENDPOINTS

Cohort 1 (Single-Agent Dose-Finding)

- Efficacy
 - BOR over the treatment period

- ORR
- DOR
- Disease Control Rate (DCR) defined as the percentage of subjects with measurable disease who have a BOR of CR or PR or stable disease (SD) or subjects with evaluable disease who have a BOR of CR or Non-CR/Non-PD. To be assigned a best overall response of SD or Non-CR/Non-PD, the time from the first administration of study drug until the date of documented SD or Non-CR/Non-PD should be ≥ 7 weeks.
- Clinical Benefit Rate (CBR) defined as the percentage of subjects with measurable disease who have a BOR of CR or PR or durable SD lasting ≥ 23 weeks or subjects with evaluable disease who have a BOR of CR or durable Non-CR/Non-PD lasting ≥ 23 weeks
- PFS defined as the time from the date of the first administration of study drug to the date of first documentation of disease progression or date of death, whichever occurs first
- TTP defined as the time from the date of the first administration of study drug until the date of first documentation of disease progression
- OS defined as the time from the date of the first administration of study drug until the date of death from any cause. Subjects who are lost to follow-up and those who are alive at the date of data cutoff will be censored at the date the subject was last known to be alive (or the data cutoff date).
- Safety
 - AEs, SAEs, clinical laboratory values, vital signs, 12-lead ECG, urine dipstick, occult blood in stool, Lansky play scores or Karnofsky performance scores, physical examination findings, and height and closure of proximal tibial plates during treatment and follow-up
- Plasma lenvatinib exposure parameters

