5.1 Study Endpoints

5.1.1 Primary Endpoints

For Cohort 1, the primary endpoint is RD of lenvatinib based on the TiTE-CRM design. While for Cohort 3A, it is RD of the combination treatment (lenvatinib + etoposide + ifosfamide).

For the three Phase 2 cohorts, the primary endpoints are:

- Cohort 2A (DTC): ORR, ie, the proportion of subjects who have a BOR of complete response (CR) or partial response (PR) for subjects with measurable disease and BOR for all subjects based on RECIST 1.1
- Cohort 2B (Osteosarcoma): PFS-4, ie, the percentage of subjects evaluable for PFS-4 who are alive and without PD at 4 months from the first dose based on RECIST 1.1. Subjects evaluable for PFS-4 includes those treated at least 4 months or those who died or radiologically progressed within 4 months after first dose.
- Cohort 3B: PFS-4

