5.4.2.1 Primary Efficacy Analyses

COHORT 2A: DTC

The primary efficacy endpoint is ORR for subjects with measurable disease and BOR for all subjects. Tumor response will be based on RECIST 1.1 and assessed every 8 weeks. The analysis will be descriptively performed on the Full Analysis Set.

COHORT 2B: SINGLE-AGENT EXPANSION

The primary efficacy endpoint is the PFS-4 rate based on RECIST 1.1. This is the proportion of subjects free of progression at 4 months. The PFS-4 rate will be estimated using the binomial proportion and the corresponding 80% and 95% exact binomial distribution CIs ([Clopper and Pearson, 1934](#)) will also be provided. The PFS-4 rate will also be tested using a null hypothesis that the PFS-4 rate is $\leq 25\%$ tested against the alternative hypothesis of a PFS-4 rate $\geq 45\%$, using the 1-sample exact test of a single proportion, at the 1-sided 0.1 level. These analyses will be performed on the lenvatinib-naïve subjects in the Full Analysis Set and the Per Protocol Analysis Set.

The PFS-4 rate will be calculated using PFS-4 evaluable subjects. These are defined as follows.

PFS-4 evaluable subjects:

- includes subjects who were treated with study medication at least 16 weeks;
- includes subjects who died or radiologically progressed within 16 weeks after the first administration of study medication. These subjects are not considered free of progression at 4 months;
- includes subjects who received anticancer treatment within 16 weeks after the first administration of study medication. These subjects are not considered free of progression at 4 months;
- excludes those who discontinue the study due to AE or reasons other than disease progression, death, or receiving anticancer treatment within 16 weeks after the first administration of study medication;
- excludes subjects administered any study medication with no baseline or no postbaseline tumor assessments.

COHORT 3B: OSTEOSARCOMA COMBINATION EXPANSION

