8.3.2 Date/Time Definitions

The following factors will be used to convert days to months or years:

1 month = 30.4375 days

- Time from first diagnosis to first dose (months) is:
(Date of first dose – Date of first diagnosis) / 30.4375
- Time from first metastatic diagnosis to first dose (months) is:
(Date of first dose – Date of first metastatic diagnosis) / 30.4375
- Time from last medication to first dose (months) is:
(Date of first dose – End date of last medication) / 30.4375
- Time from last procedure to first dose (months) is:
(Date of first dose – Start date of the last anti-cancer procedure) / 30.4375
- Time from last radiotherapy to first dose (months) is:
(Date of first dose – End date of the last radiotherapy) / 30.4375
- Time from last radioiodine therapy to first dose (months) is:
(Date of first dose – End date of the last radioiodine therapy) / 30.4375

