13.2 Summary of Efficacy Analyses

Efficacy Variable	Analysis Set	Statistical Method	Tumor Assessments
PFS-4	Full Analysis Set, Per Protocol Analysis Set	Number (percent) of subjects who are alive, free of disease progression, and did not receive anticancer medication 4 months after the first dose, and its exact 80 and 95% CIs using method of Clopper and Pearson.	Investigator
		Cohort 2B: PFS-4 rate will be tested using a Null hypothesis that PFS-4 is $\leq 25\%$ tested against the alternative hypothesis of a PFS-4 $\geq 45\%$, using the 1-sample exact test of a single proportion, at the 1-sided 0.1 level.	
ORR	Full Analysis Set, Per Protocol Analysis Set	Cohort 3B: PFS-4 rate will be tested using a Null hypothesis that PFS-4 is $\leq 25\%$ tested against the alternative hypothesis of a PFS-4 $\geq 50\%$, using the 1-sample exact test of a single proportion, at the 1-sided 0.1 level.	Investigator
PFS	Full Analysis Set, Per Protocol Analysis Set	Number (percent) of subjects (with PR + CR) and its exact 95% CI using method of Clopper and Pearson.	Investigator
OS	Full Analysis Set	KM method: Median, Q1, and Q2 PFS will be presented, with 2-sided 95% CIs (Brookmeyer and Crowley). Cumulative probability of PFS at 4 and 12 months will be presented with 2-sided 80 and 95% CIs (Greenwood using the log-log). KM plot will also be provided.	Not Applicable

Efficacy Variable	Analysis Set	Statistical Method	Tumor Assessments	
		plot will also be provided.		
BOR	Full Analysis Set, Per Protocol Analysis Set	Number (percent) and 95% exact CIs will be provided for each BOR category	Investigator	
DOR	Full Analysis Set, Per Protocol Analysis Set	KM method: Median, Q1, and Q2 PFS will be presented, with 2-sided 95% CIs (Brookmeyer and Crowley).	Investigator	
TTP	Full Analysis Set, Per Protocol Analysis Set	Kaplan-Meier method: Median, Q1, and Q2 TTP will be presented with 2-sided 95% CIs (Brookmeyer and Crowley). Cumulative probability of TTP at 4 and 12 months will be presented with 2-sided 80 and 95% CIs (Greenwood using log-log). Kaplan-Meier plot will also be provided.	Investigator	

Efficacy Variable	Analysis Set	Statistical Method	Tumor Assessments
DCR	Full Analysis Set	Number (percent) of subjects (measurable disease with CR + PR + stable disease [SD] \geq 7 weeks, evaluable disease with CR + Non-CR/Non-PD \geq 7 weeks) and its exact 95% CI using method of Clopper and Pearson.	Investigator

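### Cohort 2B's primary PFS-4 is cut at 16 weeks in SAP 5.4.2.1 but at 4 months in SAP 5.1.1, SAP 13.2 and the protocol, so an event in the gap can be classified differently by section

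*SAP*

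**What the plan says.** **Protocol 9.7.1.1** defines PFS-4 for Cohorts 2B and 3B as "the percentage of subjects who are alive and free of disease progression 4 months after the first dose based on RECIST 1.1". The stopping and success rules in Protocol 9.7.2 also refer to 4 months after the first dose.

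**SAP 5.1.1**, for Cohort 2B, keeps 4 months and adds who is evaluable: "Subjects evaluable for PFS-4 includes those treated at least 4 months or those who died or radiologically progressed within 4 months after first dose".

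**SAP 5.4.2.1** opens its Cohort 2B text in the same terms: "This is the proportion of subjects free of progression at 4 months". Its working bullets then use weeks. The evaluable group "includes subjects who were treated with study medication at least 16 weeks", and it also "includes subjects who died or radiologically progressed within 16 weeks after the first administration of study medication". New anticancer treatment within 16 weeks is handled in the same way. These early events count as not progression-free at 4 months. For Cohort 3B the parallel bullets use 18 weeks.

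**SAP 13.2** describes the endpoint as "Number (percent) of subjects who are alive, free of disease progression, and did not receive anticancer medication 4 months after the first dose".

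**SAP 8.3.2** gives the only month-to-day factor in either document: "1 month = 30.4375 days".

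**SAP Section 7** lists changes from the protocol. Neither 16 nor 18 weeks is among them.

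**The concern.** One primary endpoint has two stated cut-offs, and they govern both who is counted and who has failed. The gap is about ten days.

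Events in that gap among subjects treated for at least 16 weeks are failures under the 4-month wording but are not on the failure list in 5.4.2.1. The 25% null and 45% alternative are stated for PFS at 4 months and are tested unchanged. Activity in Cohort 2B is decided at 10 of 27, so a single reclassified subject matters if the count lies at that boundary. The trial is open-label and single-arm with investigator-read scans, so the programmer should not have to choose between the sections after outcomes are known.

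**Working it through.** **1. The cut-offs in days**

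- SAP 5.4.2.1, Cohort 2B: 16 × 7 = 112 days.
- SAP 5.1.1, SAP 13.2 and Protocol 9.7.1.1: 4 months. None prints a day count. With the SAP 8.3.2 factor, 4 × 30.4375 = 121.75 days.
- SAP 5.4.2.1, Cohort 3B: 18 × 7 = 126 days.
- Differences from 4 months: 121.75 − 112 = 9.75 days early for 2B; 126 − 121.75 = 4.25 days late for 3B.

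**2. How each section treats a Cohort 2B subject in the gap (about days 113–121)**

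| Case | SAP 5.4.2.1 bullets | SAP 5.1.1 | SAP 13.2 | Protocol 9.7.1.1 |
|---|---|---|---|---|
| Treated ≥ 16 weeks, dies day 116 | Evaluable, not a listed failure | Failure | Failure | Failure |
| Treated ≥ 16 weeks, late or unscheduled scan shows PD on day 118 | Evaluable, not a listed failure | Failure | Failure | Failure |
| Treated ≥ 16 weeks, new anticancer therapy on day 118 | Evaluable, not a listed failure | Not mentioned | Failure | Not mentioned here |
| Stops treatment event-free on day 115 | Evaluable | Not evaluable | Silent on evaluability | Silent on evaluability |

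The first two rows change the numerator. The last changes the denominator.

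**3. The plan's own design figure**

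Inputs from SAP Section 4 and Protocol 9.7.2: continue if at least 5 of 15, active if at least 10 of 27, p0 = 25%, p1 = 45%, one-sided α = 0.1, power 80%.

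P(active | p) = Σ over x = 5 to 15 of P(Bin(15, p) = x) × P(Bin(12, p) ≥ 10 − x)

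- p = 0.25: 0.0973
- p = 0.45: 0.801

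A full search for Simon's optimal design returns exactly 5/15 and 10/27, so the stated design reproduces.

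**4. How much slack the rule has**

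The same formula at p = 0.255 gives 0.108. Half a percentage point is 27 × 0.005 = 0.135 of a subject, and it already takes the rate above 0.10.

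**5. Illustration of a shifted reading time**

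The documents give no curve shape, so this is an assumption. With a constant hazard observed continuously, a rate of 25% at day 121.75 becomes 0.25^(112/121.75) = 0.279 at day 112.

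- Expected events in the gap: 27 × (0.279 − 0.250) ≈ 0.8 subjects.
- P(active) at 0.279: 0.172.

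Letting the curve bend, with S(112) = 0.25^((112/121.75)^k), k = 0.5 gives 0.131 and k = 2 gives 0.273. The 0.172 figure is therefore not an upper bound.

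**6. Why the real number is probably smaller**

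Protocol Table 8 puts scans every 8 weeks, within the due week. The second on-treatment scan is due by about day 112 and the next in Week 24. Recorded progression on days 113–121 can come only from late or unscheduled scans. Deaths do not depend on scan timing. If all scans are on time and nobody dies or starts new therapy in the gap, no subject's success or failure changes.

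**The case against.** The strongest reply is that 16 weeks is simply the working form of 4 months. It equals four 28-day cycles and the second 8-weekly scan, and 18 weeks is the third 6-weekly scan in Cohort 3B. The 5.4.2.1 bullets link events within 16 weeks to 4-month status, and the PFS censoring text in SAP 5.4.2.2 repeats Week 16 and Week 18. The protocol leaves analytical detail to the SAP, and the SAP 8.3.2 factor is applied there only to pre-treatment intervals. This is a plausible account of the intent. It does not remove the conflict, because SAP 5.1.1 states 4 months for the same two limbs and no section says that 4 months means Week 16.

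A reader might infer three stronger things that the documents do not support:

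- **That the shorter cut-off was chosen to favour the drug.** In Cohort 3B the same approach runs past 4 months and works the other way, which points to scan alignment.
- **That every event in the gap is scored as a success.** The bullets imply this only for subjects treated for at least 16 weeks, and the section's opening sentence still says 4 months. A subject who left the study for an adverse event before Week 16 and died on day 116 may be excluded instead. New anticancer therapy in the gap is an explicit failure only in SAP 13.2; under the protocol it becomes progression only through Section 9.4.8.2.
- **That the false-positive rate is 17%.** That needs a continuously observed constant hazard and a null calibrated to day 121.75. The documents give no day count for the 25%.

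The planned Kaplan-Meier 4-month PFS estimate (SAP 5.4.2.2) is a useful cross-check, but it is a secondary analysis and does not settle the primary rule. It could also count a death that the primary rate does not.

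**Conclusion.** The conflict is real and concerns a primary-endpoint rule: two stated rules give different numerators and denominators. It should be corrected before database lock.

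The likely effect is zero to about one subject of 27. The upper part of that range rests on the constant-hazard assumption, and the lower part on punctual Week 16 scans with no deaths or new therapy in the gap. Among subjects treated for at least 16 weeks, the direction is towards success. The conclusion would change only if the count lies at the boundary, where 9 of 27 is not active and 10 of 27 is. The case for acting is the rule's lack of slack (0.097 at 25%, 0.108 at 25.5%) and the low cost of removing the ambiguity. The 4-month day count rests on applying the SAP 8.3.2 factor to this endpoint, which the SAP does not itself do.

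**What to change.** Before database lock, set one cut-off in days for each cohort and use it identically in SAP 5.1.1, 5.4.2.1 and 13.2. The choice is the sponsor's:

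- **(a)** In Cohort 2B, count PD, death or new anticancer therapy through 4 months (day 122) as failure. Say which treatment duration makes a subject evaluable, so that 5.1.1 and 5.4.2.1 agree on the denominator, and settle the Cohort 3B cut-off in the same way.
- **(b)** Declare Week 16 (2B) and Week 18 (3B) as the definition of PFS-4 in SAP 5.1.1, 13.2 and Section 7. Add a scan window so that a late Week 16 scan showing PD counts as a failure, and state that the 25% and 45% rates are applied at that landmark.

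The cost is SAP wording and one programming cut-off, using data already collected. The downside is that the observed PFS-4 rate may be slightly lower.

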9.5.5 Completion/Discontinuation of Subjects

A subject (or subject's parent or guardian) may elect to discontinue study drug at any time for safety, medical, or personal reasons. Subjects who choose to discontinue study drug prior to disease progression will be followed in the post-study treatment follow-up period and continue to undergo regularly scheduled disease assessment until documentation of disease progression or start of an alternative anticancer treatment. All subjects who discontinue study drug will be followed for overall survival and all post progression cancer treatments administered will be recorded. Subjects may at any time withdraw consent for further study participation. No further data will be collected on subjects once consent has been withdrawn. All subjects who discontinue the study are to complete the study's early discontinuation procedures indicated in the Schedule of Assessments ([Table 7](#), [Table 8](#), and [Table 9](#)).

The investigator will promptly explain to the subject (or subject's parent or guardian) involved that the study will be discontinued for that subject and provide appropriate medical treatment and other necessary measures for the subject. A subject who has ceased to return for visits will be followed up by mail, phone, or other means to gather information such as the reason for failure to return, the status of treatment compliance, the presence or absence of AEs, and clinical courses of signs and symptoms.

Subjects who discontinue early from the study will be discontinued for 1 of these primary reasons: AE(s), lost to follow-up, subject choice, progression of disease, withdrawal of consent, pregnancy, study terminated by sponsor, or administrative/other. In addition to

the primary reason, the subject may indicate 1 or more secondary reason(s) for discontinuation. Study disposition information will be collected on the Subject Disposition CRF.

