The primary efficacy endpoint is the PFS-4 rate based on RECIST 1.1. This is the proportion of subjects free of progression free at 4 months. The PFS-4 rate will be estimated using the binomial proportion along with the corresponding exact binomial 80% and 95% CIs. The PFS-4 rate will be tested using a null hypothesis that PFS-4 rate is $\leq 25\%$ tested against the alternative hypothesis of a PFS-4 rate $\geq 50\%$, using the 1-sample exact test of a single proportion, at the 1-sided 0.1 level. This analysis will be performed on the lenvatinib-naïve subjects in Full Analysis Set and Per Protocol Analysis Set, while subjects enrolled from Cohorts 1 and 2B will be summarized only as appropriate.

The PFS-4 rate will be analyzed using PFS-4 evaluable subjects. These are defined as follows.

PFS-4 evaluable subjects:

- includes subjects who were treated with study medication at least 18 weeks
- includes subjects who died or radiologically progressed within 18 weeks after the first administration of study medication. These subjects are not considered free of progression at 4 months.
- includes subjects who received anticancer treatment within 18 weeks after the first administration of study medication. These subjects are not considered free of progression at 4 months.
- excludes those who discontinue the study due to AE or other reasons than disease progression, death , or receiving anticancer treatment within 18 weeks after the first administration of study medication
- excludes subjects administered any study medication but had no baseline or no postbaseline tumor assessments.

SURGICALLY REMOVED LESIONS

For Cohorts 2B, 3A and 3B, removal of existing (not new) osteosarcoma metastatic lesion(s) is permitted after the completion of the first 4 months of the treatment period without PD. The time points for tumor response assessment after tumor removal will be considered ‘Not Evaluable’ unless the tumor response is considered PD for the following reasons:

- appearance of an unequivocal new lesion
- unequivocal progression of non-target lesions or target lesions

Lesions removed before the first 4 months are permitted only in the case of PD.

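### Subjects who stop early for progression without radiologic PD have no defined status in the PFS-4 rules, or are excluded, so some treatment failures can leave the primary denominator

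*SAP*

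**What the plan says.** SAP 5.4.2.1 calculates the PFS-4 rate on evaluable subjects and defines them by five bullets. For Cohort 2B:

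1. Included: "includes subjects who were treated with study medication at least 16 weeks".
2. Included as a failure: "includes subjects who died or radiologically progressed within 16 weeks after the first administration of study medication".
3. Included as a failure: "includes subjects who received anticancer treatment within 16 weeks after the first administration of study medication".
4. Excluded: "excludes those who discontinue the study due to AE or reasons other than disease progression, death, or receiving anticancer treatment within 16 weeks".
5. Excluded: "excludes subjects administered any study medication with no baseline or no postbaseline tumor assessments".

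Cohort 3B has the same five rules at 18 weeks; its second bullet reads "includes subjects who died or radiologically progressed within 18 weeks after the first administration of study medication". Cohort 3A (SAP 5.4.3.1) refers to the 3B definition.

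SAP 5.1.1 is shorter: "Subjects evaluable for PFS-4 includes those treated at least 4 months or those who died or radiologically progressed within 4 months after first dose". It has no category for new anticancer treatment or for progression without a scan. SAP Appendix 13.2 gives the Full and Per Protocol Analysis Sets for PFS-4 and states no evaluability filter. Protocol 9.7.1.5 places the 2B test on the Safety Analysis Set, and the 3B test on its lenvatinib-naïve subjects.

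Protocol 9.5.5 lists the primary reasons for discontinuation, among them "AE(s), lost to follow-up, subject choice, progression of disease, withdrawal of consent", and attaches no imaging condition to progression. Protocol 9.4.8.3 also refers to progression assessed by the investigator before 4 months, with the subject leaving the study for it.

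**The concern.** The second bullet requires progression to be radiologic. The fourth spares anyone who left for disease progression of any kind. Between the two sits a subject judged by the investigator to have progressed, taken off before Week 16 or 18, with a postbaseline scan but none showing PD, and alive without new therapy in the window. Such a subject has failed treatment, yet only 5.1.1 settles the status, and it does so as non-evaluable. If the subject has no postbaseline scan at all, the fifth bullet removes them outright.

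Removing failures from the denominator while keeping every success can only raise the observed rate. Secondary PFS does not recover the event: with neither radiologic PD nor death, SAP 5.4.2.2 censors at the last adequate assessment. In open-label cohorts of 27 and 15 evaluable subjects, a status settled after outcomes are known can decide the result.

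**Working it through.** **Classification under SAP 5.4.2.1.** Take a subject who stops before Week 16 (18 in 3B) for investigator-assessed progression and has no scan showing PD.

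| Further course within the window | Rule that applies | Status |
|---|---|---|
| Dies, has a postbaseline scan | Bullet 2 | Failure |
| Starts new anticancer treatment, has a postbaseline scan | Bullet 3 | Failure |
| Alive, no new therapy, no postbaseline scan | Bullet 5 | Excluded |
| Alive, no new therapy, at least one postbaseline scan | None | Undefined; non-evaluable under 5.1.1 |
| Dies or starts new therapy, no postbaseline scan | Bullet 2 or 3, and bullet 5 | Conflict; no order of precedence stated |

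The third and fourth rows are the point.

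**The plan's own figures.** Inputs from SAP section 4: for 2B, p0 = 0.25, p1 = 0.45, continue with at least 5 of 15, active with at least 10 of 27; for 3B, p0 = 0.25, p1 = 0.50, n = 15, one-sided 0.10.

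2B: P(active | p) = Σ over x = 5 to 15 of P(X1 = x) · P(X2 ≥ 10 − x), with X1 ~ Bin(15, p) and X2 ~ Bin(12, p). This gives 0.0973 at p = 0.25 and 0.8012 at p = 0.45, so the stated design reproduces.

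3B, exact test: P(X ≥ 6 | 15, 0.25) = 0.148 and P(X ≥ 7 | 15, 0.25) = 0.057, so rejection needs at least 7 of 15. (The stated 80% power at n = 15 reproduces under a normal approximation, 79.6%; the exact test has 69.6%. That is a separate matter.)

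**Effect with replacement.** Let f be the share of all subjects lost by the two routes. The documents give no value; 5%, 10% and 15% are assumed. If true PFS-4 is 25% with these subjects counted as failures, the evaluable rate is p = 0.25/(1 − f). Enrolment is taken to continue until 27 or 15 subjects are evaluable.

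| f | p | 2B type I error | 3B type I error (≥7/15) |
|---|---|---|---|
| 0 | 25.0% | 9.7% | 5.7% |
| 5% | 26.3% | 12.8% | 7.2% |
| 10% | 27.8% | 16.8% | 9.3% |
| 15% | 29.4% | 21.9% | 12.0% |

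A 15% share of all subjects is 0.15/0.75 = 20% of failures. In 2B it would need 27/0.85 ≈ 32 subjects, more than the planned maximum of 30.

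**Effect without replacement.** In 3B, 6/15 gives p = 0.148; with two such failures dropped, 6/13 gives p = 0.080. From the planned 18, 7/18 gives p = 0.139 and 7/16 gives p = 0.080.

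**The case against.** A reader might infer that every subject who progresses clinically falls outside the rules. The documents do not support that: deaths and new therapy in the window are counted as failures, and a subject without a postbaseline scan is classified, as excluded. Nor does 5.4.2.1 itself drop the residual group. The wording of its fourth bullet suggests that progressors were meant to stay in, Appendix 13.2 states no filter, and the removal comes from 5.1.1, whose wording could be read as not exhaustive.

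The group may also be small. An off-treatment tumor assessment is scheduled for 2B (Protocol Table 8) and required in 3A and 3B (Table 9, note o). Scans may be brought forward if clinically indicated, and an x-ray that clearly shows a new metastasis can document progression (Protocol 9.5.1.3). The second bullet runs from first dose, so PD found after stopping but within the window counts. The endpoint is based on RECIST 1.1, and nothing states that progression as a discontinuation reason was meant to include cases without imaging.

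The assumed shares are generous too: the 2B allowance for non-evaluable subjects from all causes is 3 of 30. A change from 9/27 (p = 0.214) to 9/23 (p = 0.096) might be read as reversing the 2B conclusion. It needs four such subjects and concerns only the exact test; nine successes never meet the rule of at least 10.

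All of this stands, and it limits the size of the problem. It does not supply a rule for the residual group or undo the exclusion of clinical progressors without a scan.

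**Conclusion.** The concern holds for two groups in Cohorts 2B and 3B, both alive without new therapy in the window after stopping early for investigator-assessed progression without radiologic PD. Those with a postbaseline scan are undefined in 5.4.2.1 and non-evaluable under 5.1.1; those without one are expressly excluded. Where they are left out, the bias in PFS-4 is upward.

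The size is unknown. The type I error figures rest on assumed shares of all subjects and on replacement to the planned evaluable number. On those terms 2B exceeds its nominal 10% at every share examined, while 3B exceeds it only at 15%. The count examples assume no replacement and should not be combined with those figures. The point merits correction before database lock, but it does not show that the planned analysis will be materially wrong.

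**What to change.** In SAP 5.1.1 and in 5.4.2.1 for 2B and 3B, state that a subject who discontinues treatment for investigator-assessed disease progression within 16 weeks (2B) or 18 weeks (3B) is evaluable and not progression-free. State also that this rule and the death and new-therapy rules take precedence over the exclusion for no postbaseline scan; without that, a clinical progressor with no scan would be both included and excluded. Cohort 3A follows through its reference to 3B. Align Appendix 13.2 with the same definition.

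Add two sensitivity analyses: PFS-4 on all treated lenvatinib-naïve subjects with non-evaluable subjects counted as failures, and PFS with these discontinuations counted as events.

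The cost is SAP text and some programming, since the reason for discontinuation is already on the CRF. The drawback is that PFS-4 may come out slightly lower and will include some progression not established by RECIST 1.1.
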